After the first two sessions, we will administer another five TILS treatments to the veterans (visits 5 – 9) with fNIRS and bbNIRS measurements taken in each visit. Thus, each veteran will receive a total of six TILS treatments. An iterative statistical analysis procedure will be implemented to determine the least number of TILS sessions that can stably up-regulate prefrontal activity, which will be considered as an optimal TILS dosage.

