### Statistical Analysis Plan

TILS/sham-induced changes in HbO2, Hb and CCO concentrations from the initial baseline will be calculated using the UCLn algorithm. We will focus on oxidized CCO concentration because it is directly related to the oxygen metabolism at the cellular level. The mean CCO changes during the treatment period will be analyzed with repeated measures ANOVA (analysis of variance), by using treatment type (TILS, sham) as a within-subject variable and sex (male, female) as an independent variable.

An iterative statistical analysis will be implemented to determine whether the  $i$ th TILS treatment ( $i \leq 6$ ) is sufficient to stably up-regulate the veteran's prefrontal activations and functioning, by interrogating the veterans' incremental changes (post-treatment minus pre-treatment) in the prefrontal activations and behavioral scores in the three memory tasks. Specifically, at the  $i$ th iteration, we will include all the data from the  $i$ th to the 6th treatments. Repeated measures ANOVA will be performed on the included data, in which the treatment number ( $i$  to 6) is a within-subject variable and sex is an independent variable. If no significant main effect of treatment number ( $p < 0.05$ , effect size  $> 0.8$ ) is found at the  $i$ th iteration in either the prefrontal hemodynamic activations or the memory task scores, it means the  $i$ th TILS treatment is sufficient to stabilize the veterans' prefrontal activity and the rest treatments are not necessary. Thus, the  $i$ th TILS treatment will be determined as the optimal dosage for treating the veterans with PTSD.

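### Read naturally, the Aim 2 stopping rule counts a significant session effect of 0.8 or less as stability, with no metric for the 0.8, so the condition can only move the named session earlier or leave it unchanged

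*SAP*

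**What the plan says.** The Protocol's last paragraph sets the aim of the iterative analysis: to "determine the least number of TILS sessions that can stably up-regulate prefrontal activity". It also says that "each veteran will receive a total of six TILS treatments", so i runs from 1 to 6.

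The second paragraph of the SAP section headed Statistical Analysis Plan gives the rule. At step i, a repeated measures ANOVA uses sessions i to 6, where "treatment number ( $i$ to 6) is a within-subject variable and sex is an independent variable". The decision follows from a null result: "If no significant main effect of treatment number ( $p < 0.05$ , effect size $> 0.8$ ) is found" at that step, "in either the prefrontal hemodynamic activations or the memory task scores", then that "treatment is sufficient to stabilize the veterans' prefrontal activity and the rest treatments are not necessary", and "TILS treatment will be determined as the optimal dosage for treating the veterans with PTSD".

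The supplied text does not say how the two conditions in the parenthesis combine, or which effect-size measure the 0.8 refers to. It sets no margin for stability.

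**The concern.** Adding an effect-size threshold to a significance test usually makes a claim harder to reach. Here the claim, that session i is enough, is reached by failing to find an effect. Making an effect harder to find therefore makes the claim easier to reach. If both conditions must hold, an ANOVA showing clear change between session i and session 6 still ends the search at i whenever the observed effect is 0.8 or less.

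This is the only decision threshold the plan states for Aim 2. Two analysts who follow the text faithfully, one taking 0.8 as a standardized difference and the other as Cohen's f, could name different sessions from the same data.

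**Working it through.** **Inputs from the documents.** Six active sessions; ANOVA on sessions i to 6 with sex as a between-subject factor; threshold p < 0.05; effect size 0.8 with no metric; search for the smallest qualifying i. The plan states no sample size, power or expected curve, so there is no figure of its own to reproduce.

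**Step 1: direction.** With p alone, step i stops when p ≥ 0.05. With both conditions required, it stops when p ≥ 0.05 or the effect is ≤ 0.8. The first set lies inside the second, so the rule with the effect-size condition stops no later. This holds for any N, metric or curve, and for either reading of how the outcomes combine.

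**Step 2: can significant effects of 0.8 or less occur?** Take 0.8 as Cohen's f. With k = 7 − i sessions, df1 = k − 1, df2 = (k − 1)(N − 2) and f² = F·df1/df2. At i=1 this gives f² = F/(N − 2), so f = 0.8 needs F = 0.64(N − 2).

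| N | Critical F, i=1 | F needed for f = 0.8 |
|---|---|---|
| 10 | 2.45 | 0.64 × 8 = 5.12 |
| 20 | 2.32 | 0.64 × 18 = 11.52 |
| 30 | 2.28 | 0.64 × 28 = 17.92 |
| 40 | 2.26 | 0.64 × 38 = 24.32 |

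At N=20 significance begins at f = √(2.32/18) = 0.36. Everything from 0.36 to 0.80 is significant yet would count as no effect; at f = 0.8 the p-value is about 1e-8. At N=10 the p-value at f = 0.8 is about 0.001.

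**Step 3: how far the named session moves.** Illustration only. Assumed: one outcome, two equal sex groups with no sex effect, total SD 1, compound symmetry, mean increments of 0, 0.33, 0.67, 1, 1, 1 SD over sessions 1 to 6 (plateau at session 4), and 6000 replicates per cell. The rule is run for i = 1 to 5, with session 6 recorded if all five steps find an effect, since only one session remains at i=6. Mean named session:

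| Correlation | N | p alone | and range > 0.8 total SD | and f > 0.8 |
|---|---|---|---|---|
| 0.5 | 10 | 2.56 | 2.45 | 1.51 |
| 0.5 | 20 | 3.18 | 2.53 | 1.14 |
| 0.5 | 30 | 3.45 | 2.45 | 1.05 |
| 0.5 | 40 | 3.61 | 2.38 | 1.02 |
| 0 | 10 | 1.93 | 1.93 | 1.14 |
| 0 | 20 | 2.63 | 2.58 | 1.01 |
| 0.7 | 10 | 2.99 | 2.55 | 2.10 |
| 0.7 | 20 | 3.50 | 2.44 | 1.72 |

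No run moved later. At N=20 and correlation 0.5, p alone is 4 − 3.18 = 0.82 sessions before the plateau. The range condition adds 3.18 − 2.53 = 0.65 and f adds 3.18 − 1.14 = 2.04. At N=10 and correlation 0.5 the range condition adds only 2.56 − 2.45 = 0.11.

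**Step 4: a second set-up.** Two outcomes, a 1.5 SD rise to a plateau at session 4, N=20, 1500 replicates. If an effect in any outcome blocks the declaration, the means are 3.98 (p alone), 3.42 (standardized range) and 2.42 (f). If all outcomes must show an effect to block it, they are 3.35, 2.96 and 1.90. The direction is the same.

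**Step 5: flat curve.** With one outcome and truly flat increments, session 1 is the right answer. It is named in 0.95 of runs with p alone and in 0.95 to 1.00 with the added condition, which then does no harm.

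**The case against.** The strongest reply is that requiring a change to be large before it counts as instability is simply how a tolerance works. That stands. A reader might infer that the rule is inverted, or that it is biased in a way no amount of data would cure. The documents do not support this, because they never say that any non-zero change must count. In the assumed curve the remaining rise after session 2 is 1 − 0.33 = 0.67 SD, inside a 0.8 SD tolerance. Under that tolerance session 2 is the correct answer, and the range rule settles there (mean about 2.1 at N=200). Its distance from session 4 therefore largely reflects a different target. The same defence is weak for Cohen's f, where the rule sets aside very strong evidence of change.

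The effect-size condition also protects against false late naming when several outcomes are tested. Assume four independent outcomes, any of which blocks the declaration, with N=20 and correlation 0.5. On a flat curve, p alone correctly names session 1 in about 0.82 of runs (0.95⁴ = 0.81), against 0.96 with the total-SD condition. With the plateau at session 4, p alone overshoots in about 17% of runs, against 1%. This stands as a limit on any remedy that merely deletes the condition.

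The parenthesis might also be read otherwise. If 0.8 is only descriptive, the rule is p alone and the loosening does not arise. If either condition suffices, the session could only move later (at most 3 of 1500 runs in any setting tried). That second reading fits less well, because the parenthesis qualifies the word significant. The text settles neither.

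Finally, p alone also leans early. At N=10 with correlation 0 to 0.5, nearly all the early naming comes from reading non-significance as stability.

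**Conclusion.** The point holds on the joint reading of the parenthesis. The rule as written can record a clear, significant session effect as stability and name a session on that basis. The direction is a matter of logic; the size is not established. In the illustrative N=20, correlation 0.5 case the mean falls from about 3.2 to 2.5 under a total-SD range and to 1.1 under f. Other assumed values of N and correlation give shifts from none to more than two sessions. The fault lies in a threshold with no metric, applied to a point estimate, inside a trigger that acts on a null result; having a tolerance is not itself a fault.

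A reader might go further and conclude that the trial will name too early a session. The documents do not allow that: they give no sample size, variance, correlation, session curve or metric, and with flat increments session 1 would be right. The matter should be fixed because it can decide the Aim 2 answer. Confidence is medium, since the role of 0.8 is inferred.

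**What to change.** 1. If 0.8 is not part of the trigger, say so in one clause and name its metric.
2. If it is part of the trigger, remove it, so that a significant main effect of treatment number blocks a declaration of sufficiency. State a multiplicity adjustment across the activation and memory-task outcomes and how those outcomes combine. Report the effect size with its metric and a confidence interval. Word a null result as no further change detected.
3. If 0.8 is meant as a tolerance, state it as a pre-specified margin with its metric. Declare session i sufficient only when the confidence intervals for session i against each later session lie inside it.

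Options 1 and 2 need a few sentences and no new data. Under option 2 later sessions are named more often, some falsely if outcomes are not adjusted for. With four independent outcomes tested at 0.05/4 = 0.0125 each, the flat-curve figure would return to about 0.9875⁴ = 0.95. A stricter level also makes null results more frequent, so early naming at small N remains and may grow.

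Option 3 costs more, because the sponsor must justify a margin for each outcome, and small samples may confirm nothing. In the same plateau case (correlation 0.5, 90% intervals), an illustrative 0.5 SD margin confirms no session in 93%, 54%, 22% and 8% of runs at N=10, 20, 30 and 40. A 0.8 SD margin confirms none in 39% at N=10 and 2% at N=20.

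### The dosage rule reads a non-significant test of treatment number as proof that session i is sufficient, so an early, insufficient session can be named optimal with uncontrolled probability

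*SAP*

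**What the plan says.** The Protocol (Study Protocol, last paragraph) sets the aim of the second part of the trial: to "determine the least number of TILS sessions that can stably up-regulate prefrontal activity". It also states that "each veteran will receive a total of six TILS treatments".

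The SAP (Statistical Analysis Plan, second paragraph) gives the rule. The outcomes are the veterans' "incremental changes (post-treatment minus pre-treatment) in the prefrontal activations and behavioral scores in the three memory tasks". At iteration i the data from treatments i to 6 are kept. "Repeated measures ANOVA will be performed on the included data", with treatment number within subject and sex between subjects. The significance criterion is p below 0.05 together with an effect size above 0.8; the effect-size metric is not named.

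The decision follows directly. "If no significant main effect of treatment number" appears, the SAP concludes that the ith "TILS treatment is sufficient to stabilize the veterans' prefrontal activity and the rest treatments are not necessary", and that the ith "TILS treatment will be determined as the optimal dosage for treating the veterans with PTSD".

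Neither document, as supplied, adds an equivalence margin, a confidence interval for later sessions minus session i, the power of this test, or a requirement that the session-i increment be above zero.

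**The concern.** A positive claim, that session i is enough, is drawn from a failure to reject. That failure can arise because sessions i to 6 really are alike, or because the test could not see the difference between them. The rule cannot tell these apart. It also starts at i = 1 and stops at the first failure, so each missed difference is recorded as evidence for an earlier session.

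This rule is the whole basis for the dosage answer. The chance that it names a session whose effect is still short of the later ones is neither stated nor limited.

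**Working it through.** The supplied text gives no figure to reproduce, so this is an illustration of the written rule.

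**From the documents:** six sessions; ANOVA on sessions i to 6 with sex as a between-subject factor; threshold p < 0.05, with effect size > 0.8 as a possible second condition.

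**Assumed:** one outcome; within-veteran SD of an increment = 1; independent sessions; two sex groups; N from 6 to 100; session 1 falls d = 0.5 SD short of five equal later sessions.

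**Step 1: p < 0.05 alone.** At i = 1 the F test has df1 = 5 and df2 = 5(N − 2). The six means have a sum of squared deviations of d² × 5/6, so the noncentrality is λ = N × 0.25 × 5/6. Session 1 is named when F does not exceed its 5% critical value.

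**Step 2: effect size > 0.8 also required.** Take Cohen's f with f² = SS(effect)/SS(error) = 5F/df2. Then f > 0.8 means F > 0.64 × df2/5 = 0.64(N − 2). Session 1 is named unless F exceeds the larger of the two thresholds.

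| N | λ | df2 | Critical F | Session 1 named, p only | F needed for f > 0.8 | Session 1 named, both required |
|---|---|---|---|---|---|---|
| 6 | 1.25 | 20 | 2.71 | 90% | 2.56 | 90% |
| 10 | 2.08 | 40 | 2.45 | 85% | 5.12 | 99% |
| 20 | 4.17 | 90 | 2.32 | 71% | 11.52 | >99% |
| 30 | 6.25 | 140 | 2.28 | 57% | 17.92 | >99% |
| 60 | 12.50 | 290 | 2.25 | 22% | 37.12 | >99% |
| 100 | 20.83 | 490 | 2.23 | 4% | 62.72 | >99% |

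With sex left out of the model, df2 = 25 at N = 6 and the last column there becomes 95%.

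**Step 3: other shapes, p only, N = 20.**
- Increments rise evenly from 0 to 1 SD and never plateau. The sum of squared deviations is 0.7, so λ = 14, and session 1 is named in 19% of trials. Doubling the noise gives λ = 3.5 and 76%.
- Increments are 0, 0.2, 0.4, 0.6, 0.6, 0.6 SD (a true plateau at session 4) with between-session correlation 0.5. In simulation session 1 is named in 23% of trials, and some session before the fourth in 89%. At N = 10 the figures are 58% and 93%.
- TILS does nothing at any session. The test is then non-significant, and session 1 is named, in 1 − 0.05 = 95% of trials at every N.

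**Step 4: what a margin-based criterion would give.** Let D = mean increment of the later sessions minus the increment of session i. At i = 1, SE = √((1 + 1/5)/N) = √(1.2/N), which is 0.346, 0.245, 0.200 and 0.141 at N = 10, 20, 30 and 60. Take an illustrative margin of 0.5 SD and require the two-sided 90% interval to lie inside ±0.5.
- True shortfall equal to the margin: the criterion is met at session 1 in at most 5% of trials. This holds by construction.
- No true shortfall: it is met in 27% to 30% of trials at N = 20, 57% to 60% at N = 30 and 94% at N = 60. The lower figures use each veteran's own contrast as the error term, the higher ones the pooled ANOVA error.
- At N = 10 the expected half-width with pooled error is 1.684 × 0.346 = 0.58, already wider than the margin, so the criterion would almost never be met.

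**The case against.** **Sample size.** A reader might infer that a smaller trial always names fewer sessions, and that a larger one cures the problem. The documents do not support that without a condition. It holds if p < 0.05 alone decides. The SAP places an effect-size threshold beside the p-value, and if both are required the pattern can flatten or reverse, as the last column of the table shows. If the metric is instead the largest mean difference over the SD, the plateau-at-4 case gives session 1 in 77% of trials at N = 6, 54% at N = 15 and 93% at N = 100, which is not monotone. This objection stands. It removes the general sample-size claim but not the defect, since the second condition makes non-significance easier to obtain.

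**Single outcome.** The rule covers prefrontal activations and memory scores, and its either/or wording leaves open whether one or both must be non-significant. With two independent outcomes and the N = 20 p-only figure, session 1 would be named in 0.714² = 51% of trials if both must be non-significant, or 1 − 0.286² = 92% if one is enough. The percentages therefore move in either direction. The inference is faulty under both readings.

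**Unknown N.** Part of the SAP was not in the text reviewed, so the absence of a sample size is not held against the plan. The true error rate cannot be fixed from this text. But no N turns a non-significant result into evidence of equality; N changes only how often the mistake occurs.

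**Conclusion.** The rule is wrong as written and should be changed before the dosage analysis is run. It takes non-significance as proof of sufficiency and puts no limit on the chance of naming a session that falls short.

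Under the stated assumptions, a session 1 that is 0.5 SD short is named in 85% of trials at N = 10, falling to 22% at N = 60, if p alone decides. If Cohen's f > 0.8 is also needed, it is named in about 90% or more at every N from 6 to 60. These figures rest on an assumed N, SD, trajectory, effect-size metric and single outcome, and show scale only. The logical error does not depend on them. What cannot be concluded is that the error always shrinks as the trial grows.

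**What to change.** Replace the non-significance criterion in the second paragraph of the SAP with:

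> Session i is called sufficient only if (a) the two-sided 90% confidence interval for (mean increment of sessions i+1 to 6) minus (increment of session i) lies wholly within a margin fixed before the data are analysed, and (b) the lower one-sided 95% confidence limit for the session-i increment is above zero. The rule is applied for i = 1 to 5. If no session meets it, the report states that no sufficient number of sessions was shown.

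The F test may still be reported but decides nothing. The SAP should also name the error term and say whether one or both outcome families must meet the rule.

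Both parts are needed. A one-sided upper limit alone, at N = 20 with a 0.5 SD margin, would call session 1 sufficient in 99.7% of trials when the response fades evenly from 1 SD to 0. There D = 0.4 − 1 = −0.6, which the two-sided interval in (a) is designed to reject. The existing p-only rule names session 1 in 19% of such trials. The one-sided limit would also pass session 1 in 62% of trials when TILS does nothing, whereas (b) holds that to about 5% at each session tested. The range stops at i = 5 because no later session exists to compare with session 6.

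**Cost:** SAP wording and one pre-specified margin; no new data. The 5% limits apply to each session tested, not to the whole sequence. The main downside is that a small trial may often end with no sufficient number shown: even with no true shortfall and a 0.5 SD margin, (a) is met at session 1 in only about 27% to 30% of trials at N = 20.

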Title: Transcranial Infrared Laser Stimulation (TILS) of Prefrontal Cognition in Post-traumatic Stress Disorder (PTSD)

NCT number: NCT03209882

Date: 05/15/2021

Study Protocol

Veterans with PTSD are recruited from local community. Potentially qualified veterans will first undergo a diagnostic clinical interview (visit 1). The PTSD symptom scores and other medical information collected in this visit will be reviewed immediately to determine whether eligibility criteria are met. Eligible individuals will be guided to go through an IRB-approved informed consent form that describes the study and the terms of potential participation in the study. If a person chooses to participate, s/he will be scheduled for an fNIRS screening (visit 2). This screening will confirm whether the veteran shows hypoactivations in the prefrontal cortex in the memory retrieval phase – a precondition for study inclusion.

Table 1. Experimental protocol

Aim	Visit	Task
Evaluations & screening	1	Clinical evaluation and consenting
	2	fNIRS scan
Aim 1	3–4	Pre-treatment fNIRS scan Sham or TILS; bbNIRS measurement Post-treatment fNIRS scan
Aim 2	5–9	Pre-treatment fNIRS scan TILS; bbNIRS measurement Post-treatment fNIRS scan

Veterans who pass the initial evaluations and screening will be instructed to receive once weekly TILS treatment at the same light power for seven weeks (visits 3 – 9). In fact, we will administer a sham treatment and a TILS treatment in a randomized sequence during the first two weeks (visits 3 and 4) to determine any acute neurophysiological effects of TILS compared with those induced by sham. Specifically, these effects include: 1) the prefrontal metabolic/CCO changes measured by bbNIRS during the treatment; and 2) the incremental changes of prefrontal activations and scores from three neutral memory tasks, which will be measured by fNIRS before and after the treatment (i.e., post-treatment measures minus pre-treatment measures). Then, statistical analyses will be conducted to determine the acute neurophysiological effects of TILS compared with sham.

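### A flat post-minus-pre response while weekly TILS continues does not show that the remaining treatments can be omitted, so the SAP's dosage conclusion does not follow from its rule

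*SAP*

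**What the plan says.** The final paragraph of the protocol sets the Aim 2 goal, to "determine the least number of TILS sessions that can stably up-regulate prefrontal activity", and calls that number the optimal dosage. On exposure it says "Thus, each veteran will receive a total of six TILS treatments". The only randomized element is order: "we will administer a sham treatment and a TILS treatment in a randomized sequence during the first two weeks (visits 3 and 4"). The other five TILS sessions are given to all at visits 5 to 9. Table 1 schedules an fNIRS scan before and after treatment at every visit from 3 to 9. No later visit is described.

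The second paragraph of the SAP analyses "incremental changes (post-treatment minus pre-treatment) in the prefrontal activations and behavioral scores in the three memory tasks". At iteration i, "we will include all the data from the" ith to the 6th treatment, and a repeated measures ANOVA tests the main effect of treatment number. If that effect is not significant, the SAP states that "it means the $i$ th TILS treatment is sufficient to stabilize the veterans' prefrontal activity and the rest treatments are not necessary", and takes session i as the optimal dosage.

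**The concern.** To call treatments i+1 to 6 unnecessary is to say what would happen if they were withheld. The rule draws that conclusion from data recorded while they were being given. Flat increments over sessions i to 6 show at most that the acute response to a session does not change as weekly treatment goes on. They do not say whether the benefit would hold if treatment ended at session i.

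The choice of outcome sharpens the problem. Because it is a within-visit change, a flat non-zero value means that each later session still produces the same acute gain. That is hardly evidence that the session is dispensable.

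The headline conclusion of Aim 2 is at stake. The trial could report that later sessions are dispensable when they were maintaining the effect, or still adding to it.

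**Working it through.** The documents give no sample size, standard deviation or power, so there is no planned figure to reproduce. The check has three parts.

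**1. What is observed after session i without further TILS**

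From the protocol, TILS session i falls at visit i + 3 for i = 2 to 6. Session 1 falls at visit 3 or visit 4, depending on the randomized order. If treatment ended at session i, the TILS-free time up to visit 9 would be 9 − (i + 3) = 6 − i weeks for i ≥ 2.

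| i | TILS-free weeks to visit 9 if stopped at i | TILS-free weeks actually observed after session i |
|---|---|---|
| 1 | 5 (sham first) or 6 (TILS first) | 1 (sham first) or 2 (TILS first) |
| 2 | 4 | 1 |
| 3 | 3 | 1 |
| 4 | 2 | 1 |
| 5 | 1 | 1 |
| 6 | 0 | 0 |

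The last column comes from the pre-treatment scans in Table 1. In veterans given TILS first, it also uses the sham visit (visit 4) and the pre-treatment scan at visit 5. For i = 1 to 4 the observed gap is shorter than the gap that stopping would create. For i = 5 it reaches visit 9, but not beyond. For i = 6 no treatments remain to be judged.

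**2. What the rule can see**

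The increment is d = post − pre. Assume a gain of 0.8 SD at every session (a value not in the documents).

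- *Lost before the next visit:* pre is 0 and post is 0.8 at every session, so d = 0.8 throughout. Stopping loses everything within a week.
- *Fully retained:* pre is 0, 0.8, 1.6, 2.4, 3.2, 4.0 and post is 0.8, 1.6, 2.4, 3.2, 4.0, 4.8, so again d = 0.8 throughout. Stopping after session 1 forgoes 4.8 − 0.8 = 4.0 SD.

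The increments are identical, so any test on them gives the same answer. With error-free data the rule would select session 1 in both cases, although later sessions matter in both. A flat increment of zero, meaning no effect at all, also passes.

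**3. How often the rule selects session 1**

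The rule was simulated as a one-way repeated measures ANOVA on sessions i to 6, taking the first i with p ≥ 0.05. Assumptions: residual SD 1, between-subject SD 0.5, 4,000 runs per scenario, one outcome, sex and the effect-size threshold left out.

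| Scenario | N = 10 | N = 20 | N = 40 |
|---|---|---|---|
| No effect | 0.950 | 0.950 | 0.954 |
| 0.8 SD gain, lost each week | 0.951 | 0.950 | 0.951 |
| 0.8 SD gain, fully retained | 0.952 | 0.950 | 0.948 |

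This is what a 5% test gives when the increments are truly equal (1 − 0.05 = 0.95). The second and third rows have the same increments by construction; they differ only by simulation error. If a significant effect must also exceed the 0.8 effect-size threshold, session 1 would be chosen at least as often. If both activations and memory scores must be flat, it would be chosen somewhat less often. Neither changes the equality between the rows.

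**The case against.** The best reply is that the trial does collect information on retention. Each pre-treatment scan is taken a week after the previous visit, and veterans given TILS first go two weeks without TILS after their first session. There is also a post-treatment scan at visit 9, so the sixth treatment is not left unmeasured; what is missing is a later follow-up visit. All of this stands.

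It also rules out a stronger reading. A reader might infer that the design itself cannot tell a fading effect from a lasting one. The documents do not support that. Take an assumed model in which each session closes half of the remaining deficit.

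- At 50% weekly retention the increments are 0.500, 0.375, 0.344, 0.336, 0.334, 0.333.
- At 100% retention they are 0.50, 0.25, 0.125, 0.063, 0.031, 0.016.

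The second series shrinks visibly, so the planned endpoint itself separates these two cases. The pre-treatment scan at session 4 would separate them too: 0.656 × 0.5 = 0.328 against 0.875.

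Under 50% retention, stopping after session 3 would take the gain from 0.656 to 0.656 × 0.5³ = 0.08 by visit 9. That shows what could be lost under assumed values. It does not show that the cases are indistinguishable.

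The reply does not rescue the SAP's conclusion. The iterative analysis subtracts the pre-treatment level and never uses it as an outcome. Gaps of one to two weeks do not show the result of omitting all of sessions i+1 to 6, except at i = 5 as far as visit 9.

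**Conclusion.** The concern holds as a fault in the decision rule and its wording. A non-significant treatment-number effect on increments recorded under continued TILS does not support the statement that later treatments are unnecessary, nor the label of optimal dosage. This rests on the documents alone: six treatments for all, no group stopping early, an outcome defined as post minus pre, and no visit described after visit 9. A larger sample or an equivalence test on the same increments would not cure it.

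The size of any resulting error cannot be stated, because the documents give no figures for retention or variability. What can be said is that two situations with opposite retention, 0% and 100%, lead to the same chosen session. The simulated 95% depends on the assumed set-up; the equality of the increments needs only a constant gain per session. It would go too far to say that the data as collected hold no information on retention, since the pre-treatment scans give a short-term view.

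Whether non-significance is adequate evidence of stability is a separate matter and is not needed here.

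**What to change.** In the second paragraph of the SAP, replace the statements on sufficiency, on the remaining treatments and on optimal dosage with wording such as: *the ith treatment is the earliest from which no further change in the acute (post-minus-pre) response was detected while weekly TILS continued to six treatments.* This makes clear that any plateau is in the increment and not in the level.

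Restate the Aim 2 objective in the last paragraph of the protocol to match, and remove the inference that later treatments can be omitted. That question needs a comparison with veterans observed after fewer sessions.

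Optionally, report the pre-treatment levels by visit, which are already collected, as a description of one-week retention. For veterans given TILS first, add the two-week value after their first session.

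The cost is wording and a narrower Aim 2 claim, with no new visits, patients or measurements. No dose or number of sessions is proposed.

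### The Aim 2 session number is selected by a non-significant test and stated as established, with no measure of uncertainty

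*SAP*

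**What the plan says.** The Protocol (Study Protocol, last paragraph) says that "each veteran will receive a total of six TILS treatments". An iterative analysis then looks for the smallest number of sessions giving stable up-regulation, "which will be considered as an optimal TILS dosage".

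The SAP (Statistical Analysis Plan, second paragraph) gives the rule. At iteration i, a repeated measures ANOVA is run on the pre-to-post changes from sessions i to 6. Treatment number "is a within-subject variable and sex is an independent variable". The decision turns on the clause "If no significant main effect of treatment number", qualified by p < 0.05 and an effect size above 0.8 whose metric is not named, and applied "in either the prefrontal hemodynamic activations or the memory task scores". If the condition is met, the SAP concludes that session i is enough to stabilise "prefrontal activity and the rest treatments are not necessary", and that session "will be determined as the optimal dosage for treating the veterans with PTSD".

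Neither document, as supplied, describes a confidence interval, standard error, selection frequency or equivalence margin for the selected session.

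**The concern.** The selected session is an estimate. It comes from a data-driven search over nested subsets of the same data, and another sample of veterans could give another number. Each stop is triggered by failure to reject, which happens either because the response has levelled off or because the test has too little power to see that it has not. The plan treats both as proof of sufficiency.

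The session number is the stated result of Aim 2. Reported as planned, it would be one integer with a categorical statement that further sessions add nothing. Readers could not tell a decisive result from one in which neighbouring sessions fit the data equally well.

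**Working it through.** **Inputs from the documents.** Six TILS sessions; a repeated measures F-test of treatment number on sessions i to 6; p < 0.05 with effect size above 0.8; the first i without significance is selected. At i = 6 only one level remains, so no test is possible and session 6 is selected by default.

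**Inputs not in the supplied text, therefore assumed.** N = 12 to 40; normal data with a common within-subject SD of 1; one outcome; no dropout; p < 0.05 only (effect-size condition not modelled). The documents state no figure to reproduce.

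**Step 1: gradual rise.** Session means 0, 0.3, 0.6, 0.9, 0.9, 0.9, so the true plateau is session 4. Simulated selections, sessions 1 to 6:

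- N = 20: 18/39/31/9/2/2%
- N = 40: 1/22/53/21/2/2%

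| N | Session 4 selected | Earlier session selected |
|---|---|---|
| 12 | 5.6% | 91.3% |
| 20 | 9.4% | 87.4% |
| 30 | 14.2% | 82.0% |
| 40 | 20.5% | 75.5% |

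There were 4,000 simulated trials per N. Independent reruns agree within simulation error; including sex as a balanced factor makes no material difference.

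**Step 2: analytic check.** To select session 4 or later, the test at i = 3 must be significant, so the probability of stopping early is at least 1 minus the power of that test. The means at i = 3 are 0.6, 0.9, 0.9, 0.9, with grand mean 0.825. The sum of squared deviations is 0.225² + 3 × 0.075² = 0.0675. The noncentrality is λ = N × 0.0675, with 3 and 3(N − 1) degrees of freedom.

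| N | λ | Power at i = 3 | Early stop at least |
|---|---|---|---|
| 12 | 0.81 | 10% | 90% |
| 20 | 1.35 | 13% | 87% |
| 30 | 2.03 | 19% | 81% |
| 40 | 2.70 | 24% | 76% |

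This matches Step 1 and shows the cause: a last step of 0.3 SD is nearly invisible to the test at these sample sizes.

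**Step 3: same total rise, as a step.** Session means 0, 0, 0, 0.9, 0.9, 0.9. At i = 3 the sum of squares is 0.675² + 3 × 0.225² = 0.6075, nine times larger. For N = 20, λ = 12.15 and power is about 82%. The simulated rule selects session 4 in 47%, 76% and 94% of trials at N = 12, 20 and 40. Its accuracy therefore depends on the shape of the response, which is unknown.

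**Step 4: the effect-size condition.** On the gradual profile, reading 0.8 as Cohen's f selects session 1 in 98 to 100% of trials at N = 12 to 40; reading it as partial eta squared selects session 1 in 100%. Under those readings the choice is wrong but barely varies.

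**Step 5: what an interval would show.** For N = 20 on the gradual profile, the mean of sessions 4 to 6 minus session 3 is truly 0.3, with standard error √(1/20 + 1/60) = 0.258. An unadjusted 95% interval centred on the true value is 0.3 ± 2.00 × 0.258, or about −0.22 to 0.82 SD. It includes no further gain and also a further gain of 0.8 SD. The planned report would hide this.

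**The case against.** The strongest reply is that the figures describe an invented response and a simplified rule. That is largely right. A reader might infer that the selection varies widely across samples and is usually not the true plateau. The documents do not support this as a statement about the trial: they supply no N, SD, correlation, effect size or plateau, and part of the SAP text was removed before review. Over a wider set of assumptions with p < 0.05 alone, the probability of a correct selection ran from about 3% to 96%. It exceeded one half with larger N, a larger rise, a step rise or high within-subject correlation. Nor need the two parts of that inference occur together, as Step 4 shows.

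A second objection is that the early selection is bias from accepting a null hypothesis, which reporting spread alone does not cure. This also stands. It counts against the obvious remedy of bootstrapping veterans and re-running the rule. Resampling adds noise to the session means, so the tests reject too often within resamples. With a truly flat profile, session 1 is selected in 95% of trials, but its mean bootstrap frequency is only 62 to 66% at N = 12 to 40. On the gradual profile at N = 20, the session 6 frequency is inflated about fivefold (10% against 2%). Under the Cohen's f reading, the bootstrap would give about 97 to 100% to the wrong session at N = 20 to 40.

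Neither objection touches the core point, which rests on the text: one session number, a categorical conclusion and no described measure of uncertainty.

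**Conclusion.** The concern holds in limited form. The plan, followed exactly, can declare later sessions unnecessary because a test lacked power, and it attaches no uncertainty to that declaration. Under the assumed gradual rise (last step 0.3 within-subject SD, N = 12 to 40, one outcome, p < 0.05 only), the true plateau is selected in about 5 to 20% of trials and an earlier session in about 75 to 91%. Under a step rise of equal size it is selected in about 47 to 94%. These are scenario results and do not estimate this trial's accuracy. Their range is the reason a bare integer is not enough. The defect is in how the Aim 2 result is inferred and reported; this point takes no position on how many sessions should be given.

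**What to change.** Amend the iterative analysis paragraph of the SAP as follows, and align the last paragraph of the Protocol with it.

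- For each session i and each outcome, report the estimated difference between the later sessions and session i, with confidence intervals that are simultaneous across sessions.
- Report the selected session together with every session number those intervals do not rule out.
- Replace the statement that the remaining treatments are unnecessary with one limited to what the intervals exclude, for example that gains after session i larger than the upper limit are not compatible with the data.
- Report the rule's simulated operating characteristics at the planned N under stated response shapes, SD and correlation. Include the effect-size condition with its metric named and the way the outcomes combine.
- If bootstrap selection frequencies are shown, label them a descriptive stability check only. Re-running a significance rule in resamples over-rejects and shifts selection to later sessions, so the frequencies are not a calibrated range.

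The cost is a short SAP revision, a little more analysis and a less certain headline. Visits, treatment and data collection do not change.
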